6.2.3. Study Day and Reference Dates

Study day is calculated as the number of days from Date of First skin challenge done at Visit 1:

- Ref Date = Missing → Study Day = Missing
- Ref Date < First skin challenge Date → Study Day = Ref Date – Date of first Visit 1 Skin Challenge
- Ref Date \geq First skin challenge Date → Study Day = Ref Date – (Date of First Skin Challenge) + 1

6.2.4. Assessment Window

No Assessment Windows will be defined for analysis, and all (except Safety) summaries and analyses will be based on nominal visits. Safety summaries and analyses will use the remapped visits. Please see OPS for further details.

Unscheduled and withdrawal visits will not be slotted to an analysis timepoint, but they will be considered for worse case and maximum displays. If multiple assessments qualify for worse case or maximum, the earlier one will be used.

Acceptable windows are included in the SRM and assessments performed within these windows are not protocol deviations.

6.2.5. Multiple measurements at One Analysis Time Point

When triplicate ECG/Vital Signs assessments are taken, mean of the measurement will be calculated first and summary statistics will be based on the calculated mean. This will apply to both baseline and post baseline assessments.

For lab tests on a study day, if more than one assessment is taken on the same day from the same type of local lab, the worst case will be used.

6.2.6. Premature Withdrawals

Element	Reporting Detail
General	
 • Participant study completion (i.e. as specified in the protocol) was defined as having completed phases of the study including the follow up phone call as shown in the Schedule of Activities (see Protocol) • All available data from participants who were withdrawn from the study will be listed and all available planned data will be included in summary tables and figures, unless otherwise specified.

6.2.7. Handling of Missing data

Element	Reporting Detail
General	
 Missing data occurs when any requested data is not provided, leading to blank fields on the collection instrument: 
 These data will be indicated by the use of a ‘blank’ in participant listing displays. Unless all data for a specific visit are missing in which case the data is excluded from the table. Answers such as ‘Not applicable’ and ‘Not evaluable’ are not considered to be missing data and should be displayed as such.
Wheal and flare	
 No imputation methods will be used for missing value of the longest and orthogonal diameters
AUC	
 If there are single non-consecutive missing time points, or 2 consecutive missing time points, AUC will be calculated using trapezoidal rule (using non missing time points) If 3 or more consecutive time points are missing, AUC will be set to missing If 50% or more time points are missing, AUC will be set to missing If at least 50% points are non-missing, and the last 2 timepoints are missing, the AUC will be calculated using non-missing timepoints up to N-2
Biomarkers (IDM)	
 No imputation methods will be used for missing value.
AE	
 A worst-case scenario approach will be taken to handle missing data: if the relationship to study intervention is missing, the relationship will be “yes”, if severity is missing the severity will be set to ‘severe’, if seriousness is missing the seriousness will be set to ‘yes’

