4.2. Primary Pharmacodynamic Analyses

4.2.1. Definition of endpoint

For parts 1 and 2, the primary endpoint is the wheal response-time area under the curve (AUC) over the 2h post-challenge period following skin challenge with ascending concentrations of SP on a single day (challenge visit 1) and 2 days (challenge visits 1 and 2), respectively, expressed as mm^2/min (see OPS).

The wheal response variable will be the area in millimetres squared (mm^2) and will be calculated using the following formula for area of an ellipse (see OPS), using the longest and orthogonal diameters measured by the calliper method.

The wheal response variable will be calculated for each ascending SP concentration and each control challenge (saline and histamine) and at each timepoint during the 2h post-challenge period at challenge visit 1 (parts 1 and 2) and challenge visit 2 (part 2).

The same as above will be repeated for flare.

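### SAP 6.2.7 lets an AUC that stops at 60 or 90 min stand as the 2 h AUC; a common-window sensitivity analysis, a count of truncated values and clearer rules would cover the modest risk

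*SAP*

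**What the plan says.** SAP 4.2.1 states that "the primary endpoint is the wheal response-time area under the curve (AUC) over the 2h post-challenge period". It is derived for each SP concentration and each control, at one visit in Part 1 and two in Part 2. SAP 4.2.2.1 makes the difference between consecutive concentrations the summary measure. SAP 4.3.2.3 repeats the modelling for flare AUC.

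SAP 6.2.7 has four AUC bullets:

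1. For isolated missing readings, or two in a row, "AUC will be calculated using trapezoidal rule (using non missing time points").
2. "If 3 or more consecutive time points are missing, AUC will be set to missing".
3. "If 50% or more time points are missing, AUC will be set to missing".
4. "If at least 50% points are non-missing" and "the last 2 timepoints are missing, the AUC will be calculated using non-missing timepoints up to N-2".

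On the underlying measurements it adds: "No imputation methods will be used for missing value of the longest and orthogonal diameters".

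Protocol 1.3.3 schedules eight wheal and flare readings, at 5, 10, 15, 20, 40, 60, 90 and 120 min. Protocol 9.4.2 and SAP 4.2.2.2 base the primary analysis on the Safety population and on participants who completed their challenge visits. SAP 4.2.3 plans sensitivity analyses on priors only. SAP 4.2.1 has the AUC "expressed as mm^2/min (see OPS"), a cross-reference to a programming specification that is not among the documents.

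**The concern.** An AUC over 60 or 90 min and an AUC over 120 min measure different things unless the response has already ended. The SAP text gives no rescaling, extrapolation, flag or exclusion for a shortened AUC, so it would enter the model beside full 2 h values.

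A response still present at 60 min is to be expected. Protocol 4.2 describes resolution over about 2 h, and SAP 4.3.1 provides for disappearance later than 120 min.

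What is at stake is the estimated step between concentrations, which describes the challenge model and, in Part 2, informs the review after about 10 participants (SAP 4.7, Table 1). Truncation that falls unequally on two concentrations, or on two visits, moves that estimate.

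Separately, where two bullets give opposite answers, two programmers could derive different primary values from the same data.

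**Working it through.** The documents give no AUC value or missing-reading rate, so there is no planned figure to reproduce. The time grid and rules come from Protocol 1.3.3 and SAP 6.2.7. The response shapes, AUC ratios, numbers of truncated sites and coefficients of variation are assumptions.

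**Where the AUC can end.** With N = 8, reading N−2 is 60 min. Losing only 120 min falls under bullet 1 and ends the AUC at 90 min. It cannot end earlier than 60 min, because losing 60, 90 and 120 min is a run of three and bullet 2 applies. Treating half missing as missing, the patterns that yield an AUC are:
- ending at 60 min: 1 + 5 = 6
- ending at 90 min: 1 + 6 + 15 = 22
- ending at 120 min (including the complete record): 1 + 7 + 21 + (35 − 5) = 59

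**Loss at one site.** Assume area 0 at time 0, a linear rise to 1 at p min (p = 5 to 20) and a linear decline to 0 at 120 min. The full AUC is ½ × 120 × 1 = 60.
- 60 min cut: lost tail = ½ × 60 × 60/(120 − p), so loss = 30/(120 − p) = 26% (p = 5) to 30% (p = 20).
- 90 min cut: lost tail = ½ × 30 × 30/(120 − p), so loss = 7.5/(120 − p) = 6.5% to 7.5%.

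For p = 15 the losses are 0.286 and 0.071. Other shapes:

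| Shape after peak | 60 min cut | 90 min cut |
|---|---|---|
| Gone by 60 min | 0% | 0% |
| Gone at 90 min | 12–14% | 0% |
| Gone at 120 min | 26–30% | 6–8% |
| Half left at 120 min | 43–46% | 19–20% |
| Flat | 51–55% | 25–27% |

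Starting the AUC at 5 min changes these by at most 2 points.

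**Dividing by observed time does not repair it.** For p = 15, the mean area is 42.9/60 = 0.714 to 60 min and 60/120 = 0.5 to 120 min, which is 43% too high.

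**Effect on the consecutive difference.** Let k of n sites be cut at 60 min, R be the true AUC ratio and the loss be 0.286 (p = 15, all responses gone at 120 min).
- Higher concentration only: −(k/n) × R × 0.286/(R − 1). With n = 12 and k = 1, 2, 3: −5, −10, −14% (R = 2.0) or −10, −21, −31% (R = 1.3).
- Lower concentration only: +(k/n) × 0.286/(R − 1) = +2, +5, +7% or +8, +16, +24%.
- Equal numbers at both: −(k/n) × 0.286 = −2.4, −4.8, −7.1% at any ratio.
- n = 20, higher only: −3, −6, −9% or −6, −12, −19%.

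For scale, assume a between-site coefficient of variation of 30–60% and independent errors. The shift in standard errors is (k/12) × R × 0.286 divided by CV × √((1 + R²)/12). One truncated higher-concentration site gives about 0.1–0.25 standard errors, and two give about 0.2–0.5.

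**The 50% conflict.** Suppose 4 of 8 readings are missing, including the last two. Bullet 3 sets the AUC to missing, while bullet 4 computes it. To avoid a run of three, 60 min must be present, so the other two missing readings come from 5, 10, 15, 20 and 40 min: C(5,2) = 10 patterns. If a 0 min point counted as a ninth reading, no exact half would arise.

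**Unit.** An integral of area over time is in mm² × min and a time average is in mm². The stated unit is neither.

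**The case against.** Several points on the other side stand:

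- **Complete-case analysis.** A participant who leaves early is the obvious source of late loss, and has arguably not completed the visit. Protocol 1.1 also allows withdrawn participants to be replaced. But the complete-case set is defined by completed visits, not by readings. It does not clearly remove an isolated missed late reading, and the Safety population keeps such AUCs.
- **Rarity.** Assessments are scheduled 2 h after the last SP challenge (Protocol 1.3.2), and a participant who stops intervention stays to the end of that visit (Protocol 7.2). Late loss is therefore probably uncommon. The scenarios of 1, 2 or 3 truncated sites illustrate scale and do not predict what will happen.
- **Shapes.** The flat and half-left shapes fit poorly with a response that resolves over about 2 h. The middle rows of the table are the more relevant ones.
- **Unseen specification.** The programming specification could contain a flag or a rule for late loss.
- **Visibility.** The descriptive summaries include n, so missing late readings may show there. They would not separate truncated from full AUCs in the model.

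A reader might infer that every truncated AUC with a response still present should be set to missing in the primary model. The arithmetic does not support that. Take 12 sites, 6 gone at 60 min (AUC 30) and 6 at 120 min (AUC 60, or 42.9 if cut), with a true mean of 45. If only persistent sites lose late readings (k = 1, 2, 3), truncation biases the mean by −3.2, −6.3, −9.5%, and setting those sites to missing gives −3.0, −6.7, −11.1%. If loss is unrelated to duration, the figures are −1.6, −3.2, −4.8% and −1.5, −3.2, −5.0%. The rule helps only when durations are alike: if all last to 120 min, truncation gives −2.4, −4.8, −7.1% and the rule gives 0%. It also drops persistent responses selectively. A saline AUC set to missing would empty the covariate, which removes up to 4 SP AUCs in Part 1 or 8 in Part 2.

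**Conclusion.** The point holds, at minor severity. As written, SAP 6.2.7 produces AUCs to 60 or 90 min, and the SAP text analyses them as 2 h AUCs. A truncated value is too low when the response is still present at the cut, and correct as an integral when it has gone. The conflict between bullets 3 and 4 follows from the text for eight readings and needs no assumed shape.

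A reader might infer that the primary estimates are wrong by a quarter or more. The documents do not support that. The 26–30% applies to one truncated site under an assumed shape, and the effect on the consecutive difference depends on how many sites are cut and how unequally. Nor can this produce a false test result, since Protocol 9.1 and SAP 2 test no formal hypothesis. The risk is a modest bias in an estimate.

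The 60 and 90 min cuts rest on the current grid. Protocol 1.3.3 lets Part 2 time points change, and Protocol 4.2 lets the window reach 4 h.

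**What to change.** Change SAP 6.2.7, 4.2.1 and 4.2.3 as follows:

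1. Add a sensitivity analysis of the primary wheal model, and of the flare model, on the 0–60 min AUC for all sites, with the saline covariate over the same window. If the grid changes, use the window to N−2. State that it estimates the 0–60 min response. If the 60 min reading itself is missing but a later one is present, use the straight line between its neighbours, as the trapezoidal rule already does.
2. Report the number of AUCs ending before 120 min, by concentration and visit.
3. Where the last observed area is 0, take later areas as 0, including when only the 120 min reading is missing. The AUC is then a true 2 h value, provided that a response that has gone does not return. An integral is unchanged. Record this as an exception to the no-imputation rule.
4. Make bullets 3 and 4 agree at exactly half missing, and say whether a 0 min point counts as a reading.
5. Correct the AUC unit to match the derivation, integral or time average.

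Keep the available-data rule for the primary model. Do not replace it with one that sets only persistent truncated AUCs to missing.

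The cost is some SAP wording, one extra model run per response in each part, and a count. No new data are needed. The limit is that the 0–60 min analysis is protected from late loss but does not estimate the 2 h response. It shows whether the conclusions depend on the late readings, but does not recover them.

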6.2.7.1. Handling of Missing & Partial dates

Element	Reporting Detail
General	
 Partial dates will be displayed as captured in participant listing displays. However, where necessary, display macros may impute dates as temporary variables for sorting data in listings only. In addition, partial dates may be imputed for ‘slotting’ data to study phases or for specific analysis purposes as outlined below. Imputed partial dates will not be used to derive study day, time to onset or duration (e.g., time to onset or duration of adverse events), or elapsed time variables (e.g., time since diagnosis). In addition, imputed dates are not used for deriving the last contact date in overall survival analysis dataset.

Element	Reporting Detail
Adverse Events	
 • Imputations in the adverse events dataset are used for slotting events to the appropriate study time periods and for sorting in data listings
	
 • Partial dates for AE recorded in the CRF will be imputed using the following conventions:
Missing start day	
If study intervention start date is missing (i.e. participant did not start study intervention), then set start date = 1st of month.
 
Else if study intervention start date is not missing:
 
 ○ If month and year of start date = month and year of study intervention start date, then 
 ▪ If stop date contains a full date and stop date is earlier than study intervention start date, then set start date= 1st of month. ▪ Else set start date = study intervention start date. 
Else set start date = 1st of month.

Missing start day and month	
If study intervention start date is missing (i.e. participant did not start study intervention), then set start date = January 1.
 
Else if study intervention start date is not missing:
 
 ○ If year of start date = year of study intervention start date, then 
 ▪ If stop date contains a full date and stop date is earlier than study intervention start date, then set start date = January 1. ▪ Else set start date = study intervention start date. 
Else set start date = January 1.

Missing stop day	A '28/29/30/31' will be used for the day (dependent on the month and year)
Missing stop day and month	No Imputation

Element	Reporting Detail	
	Completely missing start/stop date	No imputation
Concomitant Medications/Medical History		
 Partial dates for any concomitant medications recorded in the CRF will be imputed using the following convention:
	Missing start day	
If study intervention start date is missing (i.e. participant did not start study Intervention), then set start date = 1st of month.
 
Else if study intervention start date is not missing:
 
 If month and year of start date = month and year of study intervention start date, then 
 If stop date contains a full date and stop date is earlier than study intervention start date, then set start date= 1st of month. Else set start date = study intervention start date. 
Else set start date = 1st of month.

	Missing start day and month	
If study intervention start date is missing (i.e. participant did not start study Intervention), then set start date = January 1.
 
Else if study intervention start date is not missing:
 
 If year of start date = year of study intervention start date, then 
 If stop date contains a full date and stop date is earlier than study intervention start date, then set start date = January 1. Else set start date = study intervention start date. 
Else set start date = January 1.

	Missing end day	A '28/29/30/31' will be used for the day (dependent on the month and year).

Element	Reporting Detail	
	Missing end day and month	A '31' will be used for the day and 'Dec' will be used for the month.
	Completely missing start/end date	No imputation
	
 The recorded partial date will be displayed in listings. 	
Age	
GSK standard IDSL algorithms will be used for calculating Age.
 
 Birth date will be presented in listings as 'YYYY'. Birth date and month will be imputed as '30th June' for calculating age since only birth year is collected. 
The reference day for age calculation will be screening visit date (Screening date should be used to derive age as per programming note in Demo table).
	

7. TRADEMARKS & ABBREVIATIONS

Trademarks of the GlaxoSmithKline Group of Companies	Trademarks not owned by the GlaxoSmithKline Group of Companies
None	SAS

Abbreviation	Description
AE	Adverse Event
GSK	GlaxoSmithKline
IDM	Intradermal Micro dialysis
IDSL	Integrated Data Standards Library (GSK Standards Library)
PCI	Potential Clinical Importance
SOC	System Organ Class
BMI	Body Mass Index
DRC	Data Review Committee
PT	Preferred Term
OPS	Output & Programming Specification
PD	Pharmacodynamic
QTcF	Frederica's QT Interval Corrected for Heart Rate
SD	Standard Deviation
SP	Substance P
ECG	Electrocardiogram
MCMC	Monte Carlo Markov Chain

